3.2.3. Elimination from Per-protocol analysis Set (PPS)

3.2.3.1. Excluded participants

A participant will be excluded from the PPS analysis under the following conditions. Please note that impact of COVID-19 on the per protocol set will be determined on a case by case basis.

Code	Condition under which the code is used	Visit (timepoints) where the code is applicable
800	Fraudulent data	All
900	Invalid ICF	Visit 1
1010	Treatment number not allocated	Visit 1
1030	Study intervention not administered at all	Visit 1
1040*	Administration of concomitant vaccine(s) forbidden in the protocol Any concomitant vaccination not foreseen by the study protocol administered in the period starting 30 days before the first dose of the study vaccine and ending at Visit 3 (Day -30 to Month 3)	Visit 1 to Visit 3
1050	Randomisation failure	All
1060	Randomisation code was broken	Visit 1 to Visit 3
1070**	Study intervention not according to protocol: - 
Participants got vaccinated with the correct study intervention but containing a lower volumeAdministration not according to protocol for reason specified by investigator other than route, side and site.Site and route of study intervention is wrong or unknown	Visit 1, Visit 2

Code	Condition under which the code is used	Visit (timepoints) where the code is applicable
	
 Wrong replacement or study intervention administered (not compatible with the vaccine regimen associated to the treatment number) 	
1080	Temperature deviated study intervention administered	Visit 1, Visit 2
1090	Expired study intervention administered	Visit 1, Visit 2
2010	Protocol violation (inclusion/exclusion criteria)	Visit 1
2040*	Administration of any medication forbidden by the protocol (refer to Section 5.2.1 and 5.2.2 of the protocol) in the period from the first dose of study intervention and ending at Visit 3 (Day 1 to Month 3)	Visit 1 to Visit 3
2050*	Underlying medical condition forbidden by the protocol Any intercurrent medical condition (IMC) (refer to section 9.3.1 of the protocol) which can affect the immune response to the study intervention during the study up to Visit 3 (Day 1 to Month 3)	Visit 1 to Visit 3
2060*	Concomitant infection related to the vaccine which may influence immune response	Visit 1 to Visit 3
2080	Participant did not comply with study intervention schedule DOSE 1 – DOSE 2 = 49-83 days	Visit 2

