6.2.2. Handling of missing data

6.2.2.1. Dates

When partially completed dates (i.e. dates missing a day and/or month) are used in calculations, the following standard rules will be applied:

- A missing day will be replaced by 15
- A missing day and month will be replaced by June 30th.

The following exceptions apply:

When partially completed dates (i.e. with missing day or month) are used in calculations, the following rules will be applied:

- Adverse event start dates with missing day:
 - If the month is not the same as the study intervention dose, then the imputed start date will be the 1st of the month
 - If the event starts in the same month as at least one of the study interventions, the flag indicating if the event occurred before or after study intervention (AE.AESTRTPT) will be used to complete the date. If ‘after vaccination’ is selected, the imputed start date will match the study intervention dose given during that month. If ‘before vaccination’ is selected, the imputed date will be one day before the study intervention dose given during that month.
 - If we cannot impute the missing parts of the date using the rule under above categories, then we need to apply Version 15 rule - 15 for the missing day and 30JUN for missing month and day.

- Adverse event start dates with missing day and month:
 - If the year is not the same as the vaccine dose, then the imputed start date will be the 1st of January.
 - If the event starts in the same year as the vaccine dose, the flag indicating if the event occurred before or after vaccination (AE.AESTRTPT) will be used to complete the date. If ‘after vaccination’ is selected, the imputed start date will match the first study intervention dose given during that year. If ‘before vaccination’ is selected, the imputed date will be one day before the first study intervention dose given during that year.
 - If we cannot impute the missing parts of the date using the rule under above categories, then we need to apply Version 15 rule - 15 for the missing day and 30JUN for missing month and day.
- Adverse event end dates with missing day: the imputed end date will be the last day of the month (30 or 31) or the study conclusion date whichever comes first.
- Adverse event end dates with missing day and month: the imputed end date will be the last day of the year (31st of December) or the study conclusion date whichever comes first.

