All incomplete concomitant medication/vaccination start/end date will follow the rules above.

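### Partial vaccination dates inherit the adverse-event rule, so a vaccine with a missing day in the calendar month before Dose 1 is nearly always dated outside code 1040's 30-day look-back

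*SAP*

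**What the plan says.** SAP 6.2.2.1 starts with standard rules ("A missing day will be replaced by 15"; 30 June if day and month are both missing) and then lists exceptions for adverse-event dates. For a start date with the day missing there are two main branches:

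- Different month from the dose: "If the month is not the same as the study intervention dose, then the imputed start date will be the 1st of the month".
- Same month as a dose: "the flag indicating if the event occurred before or after study intervention (AE.AESTRTPT) will be used to complete the date". If the flag says before, "the imputed date will be one day before the study intervention dose given during that month".

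With day and month both missing in the dose year and the flag set to before, "the imputed date will be one day before the first study intervention dose given during that year". Where no branch can be applied, the fallback is day 15 or 30 June. The section closes with "All incomplete concomitant medication/vaccination start/end date will follow the rules above".

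Code 1040 in SAP 3.2.3.1 removes from the Per Protocol Set (PPS) a participant with a forbidden vaccine "administered in the period starting 30 days before the first dose of the study vaccine and ending at Visit 3". A footnote requires review of the individual listing before the code is attributed. Protocol 5.2.2 lets licensed pneumococcal and non-replicating vaccines be given until 8 days before a dose, so their prohibited pre-dose period is about 7 days.

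**The concern.** For an adverse event after a dose, the 1st of a later month is the possible date nearest the dose, which is the cautious choice. For a vaccine given before Dose 1, the 1st of an earlier month is the possible date furthest from the dose. The same rule therefore moves the vaccine out of the look-back that code 1040 is meant to police.

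The PPS is the primary immunogenicity set (SAP 4.2), so the derived date bears on who is in the primary analysis. It also feeds the 30-day concomitant medication and vaccination tables (SAP 6.1.4 and 6.1.5). In addition, the same-month and same-year branches rest on AE.AESTRTPT, and the SAP names no counterpart for medications or vaccinations.

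**Working it through.** The plan gives no figure here, so there is nothing to reproduce. The check enumerates the calendar.

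**Inputs.** Imputation branches from SAP 6.2.2.1; look-back of 1 to 30 days before Dose 1 from code 1040; about 7 days for vaccines with the 8-day allowance (Protocol 5.2.2). Assumption: Dose 1 dates and vaccination dates are uniform over the calendar. The year is 2022; pooling 2021 to 2024 gives the same whole-window results.

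**1. When is the 1st of the preceding month within 30 days?** Only for Dose 1 on 1, 2 or 3 March, or on the 1st of May, July, October or December. That is 7/365 = 1.9% of dose dates, so the imputed date is outside for 358/365 = 98.1%.

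**2. All vaccines truly in the 30-day window, day missing.** 365 × 30 = 10,950 pairs of dose date and vaccination date.

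- Earlier calendar month: 5,577 pairs (50.9%). Captured: 3 × 28 + 4 × 30 = 204, and 204/5,577 = 3.7%. Missed: 96.3%.
- Same calendar month: 5,373 pairs (49.1%). With a flag, all are set to dose minus 1 day and captured.
- Whole window with a flag: (5,373 + 204)/10,950 = 50.9% captured, 49.1% missed.
- Whole window without a flag, same-month dates falling back to day 15: 4,317/10,950 = 39.4% captured, 60.6% missed.

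The result depends on the dose day. With a flag, the share captured is 1/30 = 3% for a dose on 2 May, 14/30 = 47% on 15 May and 24/30 = 80% on 25 May.

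**3. All vaccines in the preceding calendar month, true day uniform.** 50.2% are truly within 30 days and 1.9% are imputed there, so 48.3% are misclassified. Day 15 would misclassify 25.0%. Counting a vaccine as in the window whenever any possible date is would misclassify 47.8%, in the opposite direction.

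**4. Vaccines with the 8-day allowance (7-day window).** Of the preceding-month vaccines, 3.0% are misclassified by the SAP rule; the any-possible-date rule would misclassify 20.0%. Over the whole 7-day window with a flag, 2,219/2,555 = 86.8% are captured. However, dose minus 1 day also wrongly flags 16.0% of those given on permitted days, 8 to 61 days before the dose. Without a flag, capture falls to 588/2,555 = 23.0%.

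**5. Product ongoing at Visit 1, only the dose year known, no usable flag.** The start becomes 30 June. That is after Dose 1 for 180/365 = 49.3% of dose dates, and more than 29 days after it for 151/365 = 41.4%.

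**The case against.** The strongest reply is that the rule does not fail across the board. A reader might infer that almost every forbidden vaccine in the 30 days before Dose 1 goes undetected. The text does not support that: the same-month before branch captures every such vaccine if the flag exists, so about half of the window is caught. Nor is the error only towards keeping participants in the PPS, because dose minus 1 day can flag permitted vaccines. Code 2040 is not touched by the look-back argument, since its window starts at the first dose.

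It is also not documented that vaccinations lack a flag. SAP 6.2.3.5 counts concomitant medications and vaccinations among events, and SAP 6.2.1 describes a before/after field in the case report form for events. What stands is that the SAP names only the adverse-event variable.

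There are other safeguards. A forbidden vaccine before Dose 1 is an exclusion criterion checked at Visit 1, eligibility violations have their own code (2010), and code 1040 needs listing review. These reduce the harm. The documents do not say whether that review works from raw or imputed dates, so it cannot be assumed to see a record dated outside the window.

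Finally, the closing sentence could be read as pointing only to the standard rules. Day 15 would then apply and 8,167/10,950 = 74.6% of the window would be captured. That reading is less natural, because the sentence follows the exceptions, but the ambiguity is itself a reason to reword.

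**Conclusion.** The point holds in a narrow form. For a vaccine with a missing day in the calendar month before Dose 1, the stated rule puts the date outside the 30-day look-back for about 98% of Dose 1 dates and misses about 96% of those truly inside. Over the whole window the miss is about 49% with a before/after flag and about 61% without one. For vaccines under the 8-day allowance the 1st-of-month branch matters little.

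These figures assume uniform dates and the reading that imports the adverse-event branches. The 30 June problem arises only if no flag is available for medications and both day and month are missing.

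The effect on the primary conclusion is probably negligible. The number of partial dates is not given, and with 100 evaluable HZ/su participants the criterion is met from 70 responders, against an assumed response rate of 95%. This is a low-priority correction.

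**What to change.** Replace the closing sentence of SAP 6.2.2.1 with a separate rule for medication and vaccination dates that:

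- names the before/after flag used for these records;
- never gives a product recorded as ongoing at Visit 1 a start date after Visit 1;
- for code 1040, does not use the 1st-of-month imputation, but sends any partial date that could fall in the applicable prohibited window (30 days, or the shorter period under the 8-day allowance) to the individual-listing review already required, carried out before unblinding in line with SAP 6.1.3.

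Exclusion should not be automatic: step 3 shows that this would only reverse the error (47.8% against 48.3%), and step 4 that it would be worse for vaccines under the allowance (20.0% against 3.0%).

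The cost is a short SAP wording change, a few lines of code, a few more listings to review and possibly a few more PPS exclusions.

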6.2.2.2. Laboratory data

Missing laboratory results (immunological data) will not be replaced.

6.2.2.3. Daily recording of solicited events

6.2.2.3.1. Studies with paper diaries

For studies using paper diaries which have questions in the eCRF indicating the presence or absence of solicited events, the following rules are applicable:

- Denominators for the summary of administration site (or systemic) solicited events will be calculated using the number of participants who respond “Yes” or “No” to at least to one occurrence of the specific administration site (or systemic) events. If there is at least 1 non-missing value of temperature from day 1 to day 7 post vaccination, that occurrence will be counted as well in the denominator of systemic solicited events.
- When a specific solicited event is marked as having not occurred following a specific study dose (i.e. SDTM CE.CEOCCUR=N for the specified post-dose period for the event in question), all daily measurements will be imputed as Grade 0.
- For fever, if there are missing values and/or non-missing values of temperature from day 1 to day 7 post vaccination which are not qualifying fever definition per protocol, then that participant would not be considered for ‘Any’ rows of the solicited event summary tables.

- When a specific solicited event is marked as having occurred following a specific study dose (i.e. SDTM CE.CEOCCUR=Y for the specified post-dose period for the event in question), any missing daily recordings will be given imputed values to allow them to contribute to the 'Any' rows but not to specific grade rows of the solicited event summary tables.

The following table shows how participants contribute to each category for a specific solicited event over the Day X to Day Y post-dose period:

Solicited event category	Participants included in the calculation of the numerator
Any	All participants with at least one occurrence of the adverse event at grade 1, grade 2, or grade 3 between Day X and Day Y or with the adverse event marked as present and at least one missing daily recording between Day X and Day Y
At least grade 1	All participants with at least one occurrence of the adverse event at grade 1, grade 2, or grade 3 between Day X and Day Y
At least grade 2	All participants with at least one occurrence of the adverse event at grade 2 or grade 3 between Day X and Day Y
At least grade 3	All participants with at least one occurrence of the adverse event at grade 3 between Day X and Day Y

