**Table 16      Solicited systemic events**

Fatigue
Fever
GI symptoms †
Headache
Myalgia
Shivering

†Gastrointestinal symptoms include nausea, vomiting, diarrhoea and/or abdominal pain.

Note: participant's and/or participant's LAR(s) will be instructed to measure and record the oral temperature in the evening. If additional temperature measurements are taken at other times of the day, participants and/or participant's LAR(s) will be instructed to record the highest temperature in the diary card.

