6.2.3.8. Counting rules for occurrences of solicited events

When the occurrences of solicited events are summarized, each event recorded as having occurred during a specific period will be counted as only one occurrence regardless of the number of days on which it occurs.

Table 3 Intensity scales for solicited events

Adults (≥ 50 years)		
Event	Intensity grade	Parameter
Pain at administration site	0	None
	1	Mild: Any pain neither interfering with nor preventing normal everyday activities.
	2	Moderate: Painful when limb is moved and interferes with everyday activities.
	3	Severe: Significant pain at rest. Prevents normal everyday activities.
Redness at administration site		Greatest surface diameter in mm
Swelling at administration site		Greatest surface diameter in mm
Pruritis at administration site	0	None
	1	Mild: Itchy sensation that neither interferes with nor preventing normal everyday activities.
	2	Moderate: Itchy sensation that interferes with normal everyday activities.
	3	Severe: Itchy sensation that prevents normal everyday activities.
Temperature*		Temperature in $^{\circ}\text{C}/^{\circ}\text{F}$ (with 1 decimal)
Headache	0	None
	1	Mild: Headache that is easily tolerated
	2	Moderate: Headache that interferes with normal activity
	3	Severe: Headache that prevents normal activity
Fatigue	0	None
	1	Mild: Fatigue that is easily tolerated
	2	Moderate: Fatigue that interferes with normal activity
	3	Severe: Fatigue that prevents normal activity
Gastrointestinal symptoms	0	None
	1	Mild: Gastrointestinal symptoms that are easily tolerated
	2	Moderate: Gastrointestinal symptoms that interfere with normal activity
	3	Severe: Gastrointestinal symptoms that prevent normal activity

Adults (≥ 50 years)		
Event	Intensity grade	Parameter
Myalgia	0	None
	1	Mild: Myalgia that is easily tolerated
	2	Moderate: Myalgia that interferes with normal activity
	3	Severe: Myalgia that prevents normal activity
Shivering	0	None
	1	Shivering that is easily tolerated
	2	Shivering that interferes with normal activity
	3	Shivering that prevents normal activity

* Fever is defined as temperature $\geq 38.0^{\circ}\text{C}/100.4^{\circ}\text{F}$ regardless of the location of measurement. The preferred route for measuring temperature is oral.

The maximum intensity of injection administration site redness/swelling and fever will be scored at GSK as follows:

Intensity grade	Redness/swelling	Fever
0:	≤ 20 mm	$<38.0^{\circ}\text{C} (100.4^{\circ}\text{F})$

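### The rule for a solicited event marked 'No' is not limited to missing days, so read literally it grades a recorded fever as 0, and the SAP does not say which source prevails

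*SAP*

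**What the plan says.** SAP 6.2.2.3.1 sets the rules for daily solicited-event data from paper diaries, where the eCRF also holds a question on whether each event was present.

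- **Event marked No.** "When a specific solicited event is marked as having not occurred following a specific study dose" (CEOCCUR=N), "all daily measurements will be imputed as Grade 0".
- **Event marked Yes.** "any missing daily recordings will be given imputed values", so that those days count in *Any* but not in a specific grade row.
- **Fever, numerator.** A participant whose temperatures on Days 1 to 7 are missing, or are "non-missing values of temperature from day 1 to day 7 post vaccination which are not qualifying fever definition per protocol", is left out of *Any*.
- **Fever, denominator.** If at least one temperature was recorded on Days 1 to 7, "that occurrence will be counted as well in the denominator of systemic solicited events".

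SAP 6.2.3.8 (Table 3) covers grading: "The maximum intensity of injection administration site redness/swelling and fever will be scored at GSK as follows". Grade 0 is a temperature below 38.0°C or a diameter of 20 mm or less. Protocol Table 18 gives the same scale. Under protocol Table 16, participants "will be instructed to measure and record the oral temperature in the evening".

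**The concern.** The two companion rules are worded differently. One names missing recordings; the other names all measurements. A programmer working from the text could reasonably set every day to Grade 0 once the event is marked *No*, including days with a recorded value.

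For fever this can bite, because a temperature is asked for each evening and so can exist alongside a *No*. The event-level answer would then override a measurement that the grading table calls Grade 1 or higher. Reactogenicity is a secondary objective, and SAP 4.7.1 applies the same derivation rules to the early safety report for the Indian regulator.

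**Working it through.** The documents state no figure that depends on this rule, so there is none to reproduce. The check applies the rule to example records under two readings and then sizes the difference.

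**Inputs**

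- Fever grades (SAP Table 3, protocol Table 18): below 38.0°C is 0; 38.0 to 38.5 is 1; above 38.5 to 39.0 is 2; above 39.0 is 3.
- Redness and swelling grades (same tables): up to 20 mm is 0; above 20 to 50 is 1; above 50 to 100 is 2; above 100 is 3.
- Group size: 144 planned per group (protocol 6.3.2).
- Confidence intervals: exact Clopper-Pearson, 95% (SAP 4.1.1).

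**Step 1: grade records marked No under each reading.** Reading A is literal: every day becomes 0. Reading B sets only missing days to 0 and grades recorded values from the table.

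| Record marked No (highest value) | Reading A | Reading B |
|---|---|---|
| All temperatures missing | 0 | 0 |
| All recorded temperatures below 38.0°C | 0 | 0 |
| One temperature of 38.2°C | 0 | 1 |
| One temperature of 38.6°C | 0 | 2 |
| One temperature of 39.2°C | 0 | 3 |
| Diameter 15 mm | 0 | 0 |
| Diameter 35 mm (if recordable after No) | 0 | 1 |
| Diameter 120 mm (if recordable after No) | 0 | 3 |

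The readings differ only for a discordant record: a *No* together with a temperature of 38.0°C or more, or a diameter above 20 mm.

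**Step 2: numerator and denominator.** SAP 6.2.2.3.1 counts a participant in *Any* for at least one day at Grade 1 to 3, or for an event marked present with a missing day. Under reading A a discordant participant meets neither condition and leaves the numerator. The same participant stays in the denominator, through the *No* answer and, for fever, through the recorded temperature as well.

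**Step 3: size.** With x events among n participants, losing one moves the percentage from 100x/n to 100(x − 1)/n, a change of 100/n points. At n = 144 that is 100/144 = 0.69 points.

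For scale, suppose 0 to 3 participants carry the only fevers in a group (an assumed range):

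| Count | Percentage | 95% CI |
|---|---|---|
| 0/144 | 0% | 0 to 2.5% |
| 1/144 | 0.7% | 0.02 to 3.8% |
| 3/144 | 2.1% | 0.4 to 6.0% |

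**Step 4: direction.** Grade 0 is the lowest grade, so reading A can remove events and can never add one.

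**Step 5: other outputs.** SAP 4.5 reports fever in cumulative 0.5°C steps. If those rows use the temperatures and *Any* uses the imputed grade, one table can disagree with itself. SAP 6.2.3.6 counts duration as days at Grade 1 or higher, so a discordant day would add nothing under reading A.

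**The case against.** The best answer is that missing-only imputation was meant all along. The rule falls under "6.2.2. Handling of missing data", and to impute normally means to fill in what is absent. SAP Table 3 and protocol Table 18 grade from the value. The fever rule works from temperatures and excludes only missing or non-qualifying ones, which implies that a qualifying temperature counts. The denominator rule treats temperature as a data source of its own. All of this stands as evidence of intent. It does not settle the matter, because the fever rule is silent on a qualifying temperature with a *No*, and no section ranks the two sources.

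A second answer is that a discordant record may never occur. The diary and eCRF forms are not in the documents, so an edit check may exist. Protocol 10.1.7 provides for source data verification and sponsor quality checks, and 10.1.8 requires discrepancies between source and eCRF to be explained. These provisions mainly compare the eCRF with its source; a discordance faithfully copied from the diary could pass. The uncertainty about frequency stands.

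A reader might infer that the SAP erases recorded fevers and large local reactions. The documents do not support that. The rule assigns an analysis grade and says nothing about deleting data, and nothing shows that a diameter can be entered after a *No*.

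**Conclusion.** The point holds as a wording defect with a missing precedence rule. Followed literally, the *No* rule gives a grade that contradicts the SAP's own scale whenever a qualifying temperature was recorded. For redness and swelling this is conditional on a diameter being recordable after a *No*.

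The effect is 0.69 percentage points per discordant participant, always towards fewer events. This assumes all 144 planned participants in a group contribute diary data; with fewer, each one weighs slightly more. The number of discordant records is not in the documents and may be zero.

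A reader might go further and estimate how far the HZ/su fever rate would fall, or infer that the loss falls mainly on that group. Both need a fever rate and a discordance rate for this trial, and the documents give neither.

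Only descriptive reactogenicity results are touched, including those in the blinded early safety report. The vaccine response rate and the confirmatory GMC ratio are unaffected.

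**What to change.** Make two changes to SAP 6.2.2.3.1.

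1. In the rule for events marked as not having occurred, insert *missing* before *daily measurements*, so that only absent days are set to Grade 0.
2. Add a precedence rule, for example: *If an event is marked No but a recorded temperature or diameter meets Grade 1 or higher, the record is queried. If the value is confirmed, or the query remains unresolved, the event is graded from the measurement and counted in Any and in its grade row.*

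Querying first guards against counting a transcription error as a fever; the fallback prevents an open query from removing a measured one.

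The cost is one word and a short rule in the SAP, a check that the derivation program agrees, and queries for whatever discordant records exist. If the program already fills only missing days, the imputation step needs no change.

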4.3.3. Key secondary safety endpoints

The analyses for safety will be descriptive and based on the ES. The analyses will be performed by study group.

The results for the analysis of safety and reactogenicity will be tabulated as follows:

- Solicited administration site AEs and solicited systemic AEs
 - Number and percentage of participants reporting each solicited administration site AE (any grade, grade 3, resulting in a medically-attended visit) during the 7-day follow-up period after each dose and overall per participant and per dose will be tabulated with exact 95% CIs.
 - Number and percentage of participants reporting each solicited systemic AE (any grade, grade 3, resulting in a medically-attended visit) during the 7-day follow-up period after each dose and overall per participant and per dose will be tabulated with exact 95% CIs.
- Unsolicited AEs: Number and percentage of participants reporting unsolicited AE (any grade, grade 3, any related, grade 3 related, resulting in a medically-attended visit) within 30 days after any dose coded by the Medical Dictionary for Regulatory Activities (MedDRA) by primary system organ class (SOC) and preferred term (PT) with exact 95% CIs will be tabulated.
- SAEs and pIMDs: Number and percentage of participants reporting SAEs (any and related), fatal SAEs (any and related) and pIMDs (any and related) from Dose 1 (Day 1) up to 30 days post last dose and from Dose 1 (Day 1) up to study end coded by the MedDRA primary SOC and PT with exact 95% CIs will be tabulated.
- Listing of fatal SAEs, SAEs, pIMDs and withdrawals (from the study or from vaccination) due to AEs, SAEs, solicited and unsolicited AEs will be generated from first study intervention up to study end.
- Listing of pregnancy during the entire study period will be generated.

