4.5. Other Safety Analyses

Below are the other safety analyses planned for the final analysis and based on the ES. These analyses will be performed by study group.

- The percentage of participants with at least 1 administrative site adverse event (solicited only), with at least one systemic AE (solicited only) and with any AE (solicited only), all with onset during the solicited 7-day follow-up period, will be tabulated with exact 95% CI after each vaccine dose and overall. The same tabulations will be done for grade 3 solicited AEs.
- In the solicited systemic adverse event table, fever will be reported per 0.5°C cumulative increments.
- Duration of each solicited administrative site and systemic AE during the solicited follow-up period will be presented. Total duration of each individual solicited administrative site and systemic AE will be tabulated.
- Duration of each grade 3 solicited administrative site and systemic AE during the solicited follow-up period will be presented. Total duration of each individual solicited grade 3 administrative site and systemic AE will be tabulated.

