6.1.6. Study Intervention Compliance

The number of doses administered will be tabulated.

The number and percentage of participants who returned the diary cards and those who returned the diary cards with documentation of the presence or absence of AEs will be tabulated on the Exposed Set.

Summary of time interval between Visit 1 or 2 and Visit 2 and Visit 3 will be tabulated for the Exposed Set.

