6.2.3.6. Duration of events

The duration of an event with a start and end date will be the difference between the start and end date plus one day, i.e. an event that starts on 3 March 2018 and ends on 12 March 2018 has a duration of 10 days.

The duration of solicited events will be calculated as the sum of the individual days with the adverse event reported at grade 1 or higher during the solicited event period.

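### Should redness or swelling of 20 mm or less reach the *Any* row only when a diary day is blank?

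*SAP*

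**What the plan says.** The numerator table in SAP 6.2.2.3.1 gives two routes into *Any*. The first is a recorded day at grade 1 or above. The second is the event being ticked as present together with a gap in the diary: "or with the adverse event marked as present and at least one missing daily recording between Day X and Day Y". The *At least grade 1* category in the same table has the first route alone: "at least one occurrence of the adverse event at grade 1, grade 2, or grade 3 between Day X and Day Y". The text above the table gives the intent: when an event is marked as present, blank days are to feed *Any* and not the rows for individual grades. When an event is marked as absent, every day is set to grade 0, so blanks have no effect.

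Redness, swelling and fever are graded centrally from measurements (SAP 6.2.3.8, Table 3): "The maximum intensity of injection administration site redness/swelling and fever will be scored at GSK as follows". Diameters up to and including 20 mm are grade 0. For fever only, SAP 6.2.2.3.1 adds that if there are missing temperatures and/or recorded temperatures "which are not qualifying fever definition per protocol, then that participant would not be considered for" the *Any* rows.

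The planned summary in SAP 4.3.3 is "Number and percentage of participants reporting each solicited administration site AE (any grade, grade 3, resulting in a medically-attended visit"), after each dose and overall. Item 4 of SAP 4.7.1 has the same three rows for the blinded early safety report. SAP 4.5 adds durations, "Total duration of each individual solicited administrative site and systemic AE will be tabulated", and SAP 6.2.3.6 computes these as "the sum of the individual days with the adverse event reported at grade 1 or higher during the solicited event period".

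**The concern.** For redness and swelling, a reaction can be visible, ticked as present, and still grade 0. Such a participant fails the first route and enters *Any* only if a day is blank. Diary completeness, rather than the reaction, then decides whether the participant counts. Fever is also graded from a measurement and is protected from this, while redness and swelling are not. SAP 4.3.3 calls the row any grade, yet the second route admits people with no recorded day above grade 0, and these people have a duration of zero in the SAP 4.5 table.

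Nor does any listed output show how many people this involves. *At least grade 1* is defined but is not among the rows named in SAP 4.3.3 or 4.7.1. The diary compliance table in SAP 6.1.6 covers returned cards and "those who returned the diary cards with documentation of the presence or absence of AEs will be tabulated on the Exposed Set"; it does not count blank days. At stake are the any-grade redness and swelling rates, which are secondary descriptive safety endpoints, and the composite of at least one administration site event in SAP 4.5.

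**Working it through.** There is no stated figure to reproduce, because this is a counting rule. The check applies the rule to example diaries and then asks how large the effect could be.

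**Step 1: the rule applied literally.** The event is marked as present, and grade 0 is 20 mm or less.

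| Diameters, Day 1 to Day 7 (mm) | *Any* | *At least grade 1* | Duration (days) |
|---|---|---|---|
| 10, 10, 5, 0, 0, 0, 0 | no | no | 0 |
| 10, 10, 5, 0, 0, 0, blank | yes | no | 0 |
| all seven blank | yes | no | 0 |
| 10, 30, 5, 0, 0, 0, blank | yes | yes | 1 |

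The first two lines confirm the observation: they differ only in Day 7.

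**Step 2: what each diary establishes.** In the first line the maximum is known to be 10 mm, which is grade 0. In the second, the participant reports a reaction and the maximum over seven days is unknown. For the second participant, *Any* takes the upper reading (the blank day may have reached grade 1) and *At least grade 1* takes the lower (it did not). The two categories bracket the unknown value, which fits the stated intent that blanks feed one and not the other.

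**Step 3: size, per dose.** Let s be the share of a group with the event marked present and only diameters of 20 mm or less, p the share of daily entries left blank, and q the probability of at least one blank day in seven. The excess in *Any* is s × q. The documents give none of these, so all are assumptions; 144 is the planned group size.

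- Independent blanks: q = 1 − (1 − p)^7. At p = 0.05, q = 1 − 0.95^7 = 0.302. With s = 0.10 the excess is 0.0302, that is 3.0 points, or 4.3 of 144.
- Clustered blanks, where those with any blank average k blank days: q = 7p/k. At p = 0.05 and k = 3.5, q = 0.35/3.5 = 0.100, giving 1.0 point (1.4 of 144). At k = 6, q = 0.35/6 = 0.058, giving 0.6 points (0.8 of 144).
- With s = 0.01 and p = 0.05 the excess is 0.06 to 0.3 points, under one participant.
- Upper end: s = 0.20, p = 0.10, independent blanks. q = 1 − 0.90^7 = 0.522, giving 10.4 points (15.0 of 144).
- Lower end: s = 0 gives 0.

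These figures do not cover the overall rows across both doses.

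**Step 4: what an added row would show.** *Any* minus *At least grade 1* is exactly the number counted only through a blank day. It mixes recorded small reactions with diaries that hold no diameter at all. It also says nothing about small reactions in complete diaries. With s = 0.10 and p = 0.05 (independent), 0.10 × 144 = 14.4 people have small reactions only; 4.3 are counted and 14.4 − 4.3 = 10.1 stay unseen. The added row can err as well: if a share g truly exceed 20 mm and a fraction c of them left every such day blank, it misses g × c. Taking g = 0.10 and c = 0.20 gives 2.0 points (2.9 of 144).

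**The case for a change.** The strongest case for acting is that one rule for both groups does not ensure one effect. The excess s × q is equal across groups only if the product is equal, and the vaccine group may well have more small reactions. The difference between groups could then shift with diary habits. Fever shows that the sponsor recognised the problem of non-qualifying measurements, and the SAP does not explain why redness and swelling are left out. The row is already defined, so printing it costs almost nothing, and not knowing the size is itself a reason to show the count.

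Much of this stands as description. The rule does treat the two diaries differently, the effect need not be the same in each group, and the SAP gives no reason for the contrast with fever. The contrast has a natural reading, though: fever has an event definition (38.0 °C or above), so a lower temperature is not the event. Redness and swelling have only an intensity scale, so a 10 mm reaction marked as present is a reported event with grade 0 intensity. The protocol also requires diary training (10.3.8) and source data verification (10.1.7), which should limit blank days. The lists in SAP 4.3.3 and 4.7.1 give contents rather than table layouts, so the row may be printed anyway. The daily entries are the input to the rule, so the number affected can be counted from the data without amending the plan.

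**Conclusion.** The observation is right and no change is needed. The rule is pre-specified and its purpose is stated. It resolves an unknown day in the unfavourable direction, so it can raise a group's any-grade rate but not lower it. Grade 3 rows, the vaccine response rate and the geometric mean concentration ratio are unaffected, and no hypothesis is tested on solicited events.

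The size may be zero, since it depends on whether sites mark reactions of 20 mm or less as present (the eCRF page is not in the documents) and on how often days are blank. The range of 0 to 10.4 points per dose rests wholly on assumed values: 0 to 20% small reactions only and 2 to 10% of days blank.

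Printing *At least grade 1* would leave *Any* as it is, would still hide the small reactions in complete diaries, and could itself under-count. It is a matter of display that the study team may choose when laying out the tables. If they do, a footnote splitting small recorded reactions into blank-day and complete diaries, with diaries holding no diameter shown separately, would make it informative.
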